7.6.4 Adverse Events Leading to Dose Modification

AEs leading to dose delay/reduction will be summarized by treatment group:

- Overall summary of AEs leading to dose delay/reduction by worst CTC grade (any grade, grade 3-4, grade 5) presented by SOC/PT.
- Overall summary of related AEs leading to dose delay/reduction by worst CTC grade (any grade, grade 3-4, grade 5) presented by SOC/PT.

The analysis will be conducted using the 30-day safety window.

A by-subject AEs leading to dose delay/reduction listing will be provided.

7.6.5 Adverse Events

Adverse events will be summarized by treatment group.

The following analyses will be conducted using the 30 days safety window only:

- Overall summary of any AEs by worst CTC grade (1, 2, 3, 4, 5, not reported, total) presented by SOC/PT.
- Overall summary of any AEs presented by worst CTC grade (any grade, grade 3-4, grade 5) by SOC/PT. This table will be restricted to events with an incidence greater or equal to 5% in any treatment group.
- Overall summary of drug-related AEs by worst CTC grade (1, 2, 3, 4, 5, not reported, total) presented by SOC/PT.

A by-subject AE listing will be provided. A by-subject listing of any AE requiring immune modulating medications will also be provided.

7.6.6 Select Adverse Events

Analyses will be performed by select AE category.

7.6.6.1 *Incidence of Select AE*

Select AEs will be summarized by treatment group for each category/subcategory.

The following analyses will be conducted using the 30-day safety window only:

- Overall summaries of any select AEs by worst CTC grade (any grade, grade 3-4, grade 5) presented by Category or Subcategory/PT.
- Overall summaries of any drug-related select AEs by worst CTC grade (any grade, grade 3-4, grade 5) presented by Category or Subcategory/PT.

A by-subject select AE listing will be provided.

7.6.6.2 *Time-to Onset of Select AE*

Not Applicable.

7.6.6.3 *Time-to Resolution of Select AE*

Not Applicable.

7.6.7 *Immune-Mediated Adverse Events*

IMAEs will be summarized by treatment group for each immune-mediated category / PT using the 100-day safety window:

- Overall summary of non-endocrine IMAEs by worst CTC grade (any grade, grade 3-4, grade 5) where immune modulating medication was initiated presented by Category / PT.
- Overall summary of endocrine IMAEs by worst CTC grade (any grade, grade 3-4, grade 5) presented by Category / PT.

A by-subject listing of IMAEs will be provided. By-subject listings of time-to resolution for longest IMAEs cluster (any grade and grade 3-5 in separate summaries) will also be provided.

7.6.8 *Other Events of Special Interest*

A by-subject listing of OEOSI will be provided.

7.6.9 *Multiple Events*

Not applicable.

7.6.10 *Laboratory Parameters*

The analysis population for each laboratory test is restricted to treated subjects who underwent that laboratory test. Laboratory tests (in addition to the tests specified below) with CTC criteria collected in the specific studies may also be included in the summaries.

7.6.10.1 *Hematology*

The following will be summarized by treatment group as worst CTC grade on-treatment per subject and as shift table of worst on-treatment CTC grade compared to baseline CTC grade per

subject: hemoglobin (HB), platelets, white blood counts (WBC), absolute neutrophils count (ANC) and lymphocyte count (LYMPH).

The analyses will be conducted using the 30-day safety window.

A by-subject listing of these laboratory parameters will be provided.

7.6.10.2 Serum Chemistry

The following will be summarized by treatment group as worst CTC grade on-treatment per subject and as shift table of worst on-treatment CTC grade compared to baseline CTC grade per subject: ALT, AST, alkaline phosphatase (ALP), total bilirubin and creatinine.

The analyses will be conducted using the 30-day safety window.

A by-subject listing of these laboratory parameters will be provided.

7.6.10.3 Electrolytes

The following will be summarized by treatment group as worst CTC grade on-treatment per subject and as shift table of worst on-treatment CTC grade compared to baseline CTC grade per subject: sodium (high and low), potassium (high and low), calcium (high and low), magnesium (high and low), and Glucose Serum (fasting hyperglycemia and hypoglycemia regardless of fasting status).

The analyses will be conducted using the 30-day safety window.

A by-subject listing of these laboratory parameters will be provided.

7.6.10.4 Additional Analyses

In addition, further analyses on specific laboratory parameters will be performed by treatment group:

Abnormal Hepatic Function Test

The number of subjects with the following laboratory abnormalities from on-treatment evaluations will be summarized by treatment group:

- ALT or AST > 3 x ULN, > 5 x ULN, > 10 x ULN and > 20 x ULN
- Total bilirubin > 2 x ULN
- Concurrent (within 1 day) ALT or AST > 3 x ULN and total bilirubin > 2 x ULN
- Concurrent (within 30 days) ALT or AST > 3 x ULN and total bilirubin > 2 x ULN

The analyses will be conducted using the 30-day safety window.

A by-subject listing of these specific abnormalities will be provided.

Abnormal Thyroid Function Test

The number of subjects with the following laboratory abnormalities from on-treatment evaluations will be summarized by treatment group:

- TSH value > ULN and

- with baseline TSH value \leq ULN
- with at least one FT3/FT4 test value $<$ LLN within 2-week window after the abnormal TSH test
- with all FT3/FT4 test values \geq LLN within 2-week window after the abnormal TSH test
- with FT3/FT4 missing within 2-week window after the abnormal TSH test.

- TSH $<$ LLN and
 - with baseline TSH value \geq LLN
 - with at least one FT3/FT4 test value $>$ ULN within 2-week window after the abnormal TSH test
 - with all FT3/FT4 test values \leq ULN within 2-week window after the abnormal TSH test
 - with FT3/FT4 missing within 2-week window after the abnormal TSH test

The analyses will be conducted using the 30-day safety window.

A by-subject listing of these specific abnormalities will be provided.

7.6.11 Vital Signs

Not Applicable.

7.6.12 Physical Measurements

Not Applicable.

7.6.13 Non-Protocol Medical Procedures

Not Applicable.

7.6.14 Pregnancy

Not Applicable.

7.6.15 Adverse Events By Subgroup

Not Applicable.

[REDACTED]

[REDACTED]

[REDACTED]

[REDACTED]

8 CONVENTIONS

The following conventions may be used for imputing partial dates for analyses requiring dates:

- For missing and partial adverse event onset dates, imputation will be performed using the Adverse Event Domain Requirements Specification²
- For missing and partial adverse event resolution dates, imputation will be performed as follows:
 - If only the day of the month is missing, the last day of the month will be used to replace the missing day. If the imputed date is after the death date or the last known alive date, then the latest known alive date or death date is considered as the resolution date.
 - If the day and month are missing or a date is completely missing, it will be considered as missing.
- Missing and partial non-study medication domain dates will be imputed using the derivation algorithm described in 4.1.3 of BMS Non-Study Medication Domain Requirements Specification³.
- For death dates, the following conventions will be used for imputing partial dates:
 - If only the day of the month is missing, the 1st of the month will be used to replace the missing day. The imputed date will be compared to the last known alive date and the maximum will be considered as the death date.
 - If the month or the year is missing, the death date will be imputed as the last known alive date.
 - If the date is completely missing but the reason for death is present, the death date will be imputed as the last known date alive.
- For date of progression to prior therapies, the following conventions will be used for imputing partial dates:
 - If only the day of the month is missing, the 1st of the month will be used to replace the missing day.
 - If the day and month are missing or a date is completely missing, it will be considered as missing.
- For other partial/missing dates, the following conventions were used:
 - If only the day of the month is missing, the 15th of the month will be used to replace the missing day.
 - If both the day and the month are missing, “July 1” will be used to replace the missing information.
 - If a date is completely missing, it will be considered as missing.

The following conversion factors will be used to convert days to months or years:

$$1 \text{ month} = 30.4375 \text{ days} \text{ and } 1 \text{ year} = 365.25 \text{ days.}$$

Duration (e.g. time-to onset, time-to resolution) will be calculated as follows:

$$\text{Duration} = (\text{Last date} - \text{first date} + 1)$$

Last known alive date will be defined based on all appropriate dates collected on the CRF.

All statistical analyses will be carried out using SAS (Statistical Analysis System software, SAS Institute, North Carolina, USA) unless otherwise noted.

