2.4 Protocol Amendments

Table 2.4-1: Protocol Revision History

Document	Date of Issue	Summary of change
Original Protocol	15-Aug-2017	Not applicable
Revised Protocol 01	01-Nov-2017	Update to questionnaire administration updated to align with dosing cycles. Outcome research assessment and endpoints redefined updated to align with analysis planned. TNM Staging clarified for high and intermediate risk definition. Other minor corrections, clarifications.
Revised Protocol 02	21-Feb-2018	Added exclusion of subjects with active interstitial lung disease (ILD) / pneumonitis or with a history of ILD / pneumonitis requiring steroids. Aligned thyroid testing to study visits. Added guidance for premedications for cetuximab if necessary.
Revised Protocol 03	16-Nov-2018	Enrollment in the study was closed as of 15-Oct-2018. Revised Protocol 03 covers the changes implemented to the protocol post study enrollment closure: study treatment unblinding, removal of placebo treatment, and removal of analysis of efficacy end-points and efficacy follow-up.

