are no records with indeterminant test result, then select those with unavailable result ('NOT EVALUABLE). If there are no records with unavailable test result, then select those with not reported or not available result (all other records). The latest record will be used as the baseline in the analyses. If there is more than one record for the latest date, then choose the one with the greatest specimen ID.

- Post baseline period:
 - On-treatment AEs will be defined as AEs with an onset date and time on or after the date and time of the first dose of study treatment (or with an onset date on or after the day of first dose of study treatment if time is not collected or is missing). For subjects who are off study treatment, AEs will be included if event occurred within a safety window of 30 days (or 100 days depending on the analysis) after the last dose of study treatment. No "subtracting rule" will be applied when an AE occurs both pre-treatment and post-treatment with the same preferred term and grade.
 - On-treatment evaluations (laboratory tests, pulse oximetry and vital signs) will be defined as evaluations taken after the day (and time, if collected and not missing) of first dose of study treatment. For subjects who are off study treatment, evaluations should be within a safety window of 30 days (or 100 days depending on the analysis) after the last dose of study treatment.
- For subjects who are off study treatment safety assessments will only be collected through 100 days post last dose.

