7.6.1 Deaths

Deaths will be summarized by treatment group:

- All deaths, reasons for death.
- Deaths within 30 days of last dose received, reasons for death.
- Deaths within 100 days of last dose received, reasons for death.

A by-subject listing of deaths will be provided for the all enrolled subjects population.

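### A death with a known year but a missing month is dated without using the year, so it can be placed before the recorded year and wrongly counted in the 30-day or 100-day death row

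*SAP*

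**What the plan says.** SAP Section 8 has three rules for incomplete death dates.

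- **Day missing.** The first of the recorded month is used as a provisional date, and then: "The imputed date will be compared to the last known alive date and the maximum will be considered as the death date".
- **Month or year missing.** "If the month or the year is missing, the death date will be imputed as the last known alive date".
- **Whole date missing.** "If the date is completely missing but the reason for death is present, the death date will be imputed as the last known date alive".

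The last known alive date is described only in general terms: "Last known alive date will be defined based on all appropriate dates collected on the CRF". Nothing ties it to the recorded year of death.

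Section 7.6.1 uses the death date in two rows of the deaths summary: "Deaths within 30 days of last dose received, reasons for death" and "Deaths within 100 days of last dose received, reasons for death". It also has a row for all deaths, and a by-subject listing of deaths.

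**The concern.** The three rules do not treat known information alike. If the day is missing, the recorded month and year set a floor under the imputed date. If the month is also missing, the recorded year sets no floor, and a death recorded as 2019 is handled as though nothing were known about its date. The imputed date can then fall in a year that the record itself excludes.

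This reaches a reported result because the 30-day and 100-day rows depend directly on the interval from last dose to death. The plan has no efficacy analysis (Section 6), so the safety tables are its main output. A death that certainly happened after the window could be shown as one close to treatment.

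**Working it through.** The SAP states no figure to reproduce and gives no patient dates, so every date below is assumed for illustration.

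**Notation.** L = last dose; A = last known alive date; Y = recorded year of death, month missing.

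- SAP rule (Section 8): imputed death = A.
- Year-keeping rule, built like the missing-day rule: imputed death = max(A, 1 January Y).
- Day count = imputed death − L, compared with 30 and 100 (Section 7.6.1).

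**Condition for certain misplacement.** For a window of w days, the SAP rule counts the death inside when A − L ≤ w. The death cannot have been inside when 1 January Y − L > w. Both must hold.

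**Main illustration.** L = 05-Nov-2018, A = 20-Nov-2018, Y = 2019.

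- SAP rule: 20-Nov-2018 − 05-Nov-2018 = 15 days, counted in both rows.
- Earliest date the record allows: 01-Jan-2019 − 05-Nov-2018 = 25 + 31 + 1 = 57 days. Since 57 > 30, a 30-day death is impossible.
- Day 100 is 13-Feb-2019. Since 57 ≤ 100, the year-keeping rule still counts the death in the 100-day row.

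**Further assumed cases.**

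| L | A | Y | SAP rule, day | Year-keeping rule, day | Rows that change |
|---|---|---|---|---|---|
| 05-Nov-2018 | 20-Nov-2018 | 2019 | 15 | 57 | 30-day |
| 01-May-2019 | 25-May-2019 | 2020 | 24 | 245 | 30-day and 100-day |
| 01-May-2019 | 30-Jul-2019 | 2020 | 90 | 245 | 100-day |
| 20-Dec-2018 | 10-Jan-2019 | 2019 | 21 | 21 | none |
| 20-Dec-2018 | 28-Dec-2018 | 2019 | 8 | 12 | none, though the SAP date is in the wrong year |
| 01-Feb-2019 | 01-Sep-2019 | 2020 | 212 | 334 | none, though the SAP date is in the wrong year |

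In the second case every date in 2020 lies between day 245 and day 245 + 365 = 610, yet the SAP rule gives day 24. Had the month also been recorded, say March 2020, the SAP's own missing-day rule would give 01-Mar-2020, which is day 245 + 31 + 29 = 305 and outside both windows.

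The cases with Y = 2020 assume a death after the SAP's date of 19-Oct-2019. The date of database lock is not given, so such a death may or may not be possible. The main illustration does not depend on this.

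**Comparison within Section 8.** For other dates with day and month missing, the plan keeps the year and uses 1 July. For adverse event resolution and for progression on prior therapy it sets such dates to missing. None of these rules replaces a recorded year with a date from another year.

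**The case against.** The strongest defence is that the last known alive date is a cautious choice. It draws doubtful deaths towards treatment, which is the safe direction in a safety table. That is a fair argument where the year is unknown, since nothing in the record is then contradicted. It cannot justify a date that the recorded year rules out, and the SAP does not give this reason.

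A second defence is that little turns on it. The all-deaths row is untouched, deaths are listed by subject, grade 5 events are tabulated separately in Sections 7.6.2, 7.6.3 and 7.6.5, and no test or decision rule uses these counts. This stands, and it keeps the point minor.

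A third is that the remedy is partial. It still assigns the earliest date the record allows, as the missing-day rule does, and it leaves the 100-day row unchanged in the main illustration. This also stands. The remedy removes impossible dates; it does not find the true one.

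A reader might go further and infer that the last known alive date will usually fall inside the windows, so that late deaths are routinely shown as early. Section 5.1 does say "For subjects who are off study treatment safety assessments will only be collected through 100 days post last dose", and Section 2.4 records "removal of analysis of efficacy end-points and efficacy follow-up". But neither defines the last known alive date, which rests on all suitable CRF dates, and the SAP does not show whether survival contact continues after day 100. If contact does end there, few later deaths would be recorded at all. The documents support no statement about frequency.

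**Conclusion.** The rule is wrong as written for one situation: year known, month missing. It can yield a death date before the recorded year. It can also put a death that certainly occurred later into the 30-day or 100-day row, but only when the last known alive date is inside the window and 1 January of the recorded year is outside it. The table of cases shows that an impossible date does not always change a row.

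The size cannot be stated, because the SAP gives neither the number of partial death dates nor the number of subjects per arm. It is probably small. The conclusion rests on the Section 8 wording being applied literally; no other section overrides it.

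Two stronger readings are not supported. One is that the rule misplaces late deaths in general. The other is that using the last known alive date when the year or whole date is missing is an error; showing such deaths as of unknown timing would be a presentation preference. This is a minor correction, worth making because it is simple.

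**What to change.** In SAP Section 8, split the rule for a missing month or year:

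- Year known, month missing: impute the later of the last known alive date and 1 January of the recorded year.
- Year missing, or whole date missing: keep the last known alive date, as now.

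In Section 7.6.1, state that imputed death dates will be flagged in the by-subject listing of deaths, so that a reader can see which entries in the 30-day and 100-day rows rest on imputation.

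The cost is a line or two of SAP wording and a small programming change. No new data are needed, and the all-deaths row does not change.

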9 CONTENT OF REPORTS

The analyses described in this SAP will be included in the abbreviated Clinical Study Report except where otherwise noted. Additional exploratory analyses may be performed. Refer to the Data Presentation Plan for mock-ups of all tables and listings.

10 DOCUMENT HISTORY

Table 10-1: Document Revision History

Version Number	Author(s)	Description
1.0	[name]	Initial release dated 19-Oct-2019

APPENDIX 1 TIME-TO ONSET AND TIME-TO RESOLUTION DEFINITION AND CONVENTIONS FOR SELECT ADVERSE EVENTS, IMMUNE-MEDIATED ADVERSE EVENTS AND EVENTS OF SPECIAL INTEREST

Time-to onset definition

Time-to onset of AE (any grade) for a specific category is defined as the time between the day of the first dose of study treatment and the onset date of the earliest AE (of any grade) in this category.

The time-to onset of AE (grade 3-5) for a specific category is defined similarly with an onset date corresponding to a grade 3-5 AE.

Time-to onset of drug-related AE (any grade or grade 3-5) for a specific category is defined similarly but restricted to drug-related AE.

Time-to onset for a specific subcategory is defined similarly but restricted to event of this subcategory.

Time-to resolution definition

In order to derive the time-to resolution, overlapping or contiguous AEs within a specific category or subcategory will be collapsed into what will be termed “clustered” AEs. For example, if a subject (without pre-treatment AE) experienced an AE from 1st to 5th January, another AE (with different PT but within same category) from 6th to 11th January and same AE from 10th to 12th January, these will be collapsed into one clustered AE from 1st to 12th January. [Appendix Table 1](#) is summarizing key derivation steps for each type of clustered AEs.

Time-to resolution of AE (any grade) for a specific category is defined as the longest time from onset to complete resolution or improvement to the grade at baseline among all clustered AEs experienced by the subject in this category per adverse event criteria category. Events which worsened into grade 5 events (death) or have a resolution date equal to the date of death are considered unresolved. If a clustered AE is considered as unresolved, the resolution date will be censored to the last known alive date. Improvement to the grade at baseline implies that all different events in the clustered adverse event should at least have improved to the corresponding (i.e. with same preferred term) baseline grade. This measure is defined only for subjects who experienced at least one AE in the specific category.

The time-to resolution of AE (grade 3-5) for a specific category is defined similarly with an onset date corresponding to a grade 3-5 AE.

Time-to resolution of drug-related AE (any grade or grade 3-5) for a specific category is defined similarly but restricted to drug-related AE.

The time-to resolution of AE (any grade or grade 3-5, drug-related or all) where immune modulating medication was initiated is defined similarly. For data presentation not restricted to IMAE, the additional condition that the subject started an immune modulating medication during the longest AE resolution period will be applied.

Time-to resolution for a specific subcategory is defined similarly but restricted to event of this subcategory.

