2 STUDY DESCRIPTION

2.1 Study design

CA209-9TM was a randomized, double-blinded, placebo-controlled, phase 3 study of nivolumab or nivolumab plus cisplatin, in combination with radiotherapy in subjects with cisplatin ineligible and cisplatin eligible locally advanced squamous cell carcinoma of the head and neck (LAD SCCHN).

As of 15-Oct-2018, enrollment into the study was closed. At implementation of Revised Protocol 03, the study will be unblinded and placebo treatments will no longer be given. All enrolled subjects must be re-consented prior to continuing treatment on the study.

The study consists of two independent cohorts:

- **Cohort 1** will randomize subjects who are ineligible for cisplatin chemotherapy to receive nivolumab in combination with radiotherapy (**Arm A**) or cetuximab in combination with radiotherapy (**Arm B**).
- **Cohort 2** will randomize subjects who are eligible to receive cisplatin-based therapy to receive nivolumab in combination with cisplatin and radiotherapy (**Arm C**) or cisplatin and radiotherapy (**Arm D**).

In each cohort subjects will be randomized to the two treatment arms in a 1:1 ratio and stratified

by risk group (intermediate vs. high), PD-L1 tumor expression ($\geq 1\%$ vs. $< 1\%$ or indeterminate), and ECOG PS (0 vs. 1).

Cohort 1 (cisplatin ineligible):

[figure not shown]
- **Arm A** subjects will be administered Nivolumab in combination with intensity-modulated radiation therapy (IMRT).
 1. Nivolumab 240 mg single dose will be administered at w1d1 followed by 360 mg every 3 weeks for a total of 3 doses starting at w3d1 followed by 480 mg every 4 weeks for a total of 6 doses.
 2. IMRT 70 Gy will be administered as 35 fractions starting from w3d1 over 7 weeks.
- **Arm B** subjects will be administered cetuximab in combination with IMRT.
 1. cetuximab 400 mg/m² single dose will be administered at w2d1 followed by 250 mg/m² every week for a total of 7 doses starting at w3d1.
 2. IMRT 70 Gy will be administered as 35 fractions starting from w3d1 over 7 weeks.

Cohort 2 (cisplatin eligible):

- **Arm C** subjects will be administered Nivolumab in combination with Cisplatin and IMRT.
 1. Nivolumab 240 mg single dose will be administered at w1d1 followed by 360 mg every 3 weeks for a total of 3 doses starting at w3d1 followed by 480 mg every 4 weeks for a total of 6 doses.
 2. Cisplatin 100 mg/m² will be administered every 21 days starting at w3d1 for a total of 3 doses.

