4 ENDPOINTS

4.1 Safety Endpoints

The assessment of safety will be based on the incidence of adverse events (AEs), serious adverse events (SAEs), adverse events leading to discontinuation, adverse events leading to dose modification, select adverse events (select AEs), immune-mediated AEs (IMAEs), time to onset and time to resolution of immune-related AEs, and deaths. In addition, clinical laboratory tests will be analyzed.

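### Does the longest-cluster rule in SAP Appendix 1 hide ongoing or fatal immune-mediated events behind longer resolved ones?

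*SAP*

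**What the plan says.** SAP 4.1 includes "time to onset and time to resolution of immune-related AEs" in the safety assessment. For time to resolution, the only output that the SAP specifies is in 7.6.7: "By-subject listings of time-to resolution for longest IMAEs cluster", once for any grade and once for grade 3-5. The corresponding analysis for select AEs (7.6.6.3) is marked as not applicable.

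Appendix 1 supplies the derivation. Overlapping or contiguous records in a category are merged into clusters, and the subject's value is "the longest time from onset to complete resolution or improvement to the grade at baseline among all clustered AEs experienced by the subject". A cluster counts as unresolved if it worsened to grade 5 or if its resolution date is the date of death. For such clusters, "If a clustered AE is considered as unresolved, the resolution date will be censored to the last known alive date". Section 8 adds that "Last known alive date will be defined based on all appropriate dates collected on the CRF", and it counts a duration as last date minus first date plus one.

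Section 8 also treats resolution dates with a missing day: "the last day of the month will be used to replace the missing day". If that falls after death or after the last known alive date, the date is pulled back to one of those two.

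**The concern.** Taking a maximum over a mix of complete and censored durations needs care. Death or short follow-up makes an unresolved cluster short, so ranking by observed length can pass over exactly the clusters that Appendix 1 takes trouble to class as unresolved. Strictly, if one cluster resolved after 61 days and another is still open at 20 days, the subject's longest duration is known only to be at least 61 days.

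If the listing were read as the subject's overall outcome in that category, someone with an ongoing or fatal immune-mediated event could be taken for resolved, in the one output that serves a named safety measure. The missing tie rule adds to the impression of an unfinished definition.

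A smaller point sits beside it. An event recorded as resolved, with only the day missing, can end up with a resolution date equal to the death date under Section 8. Appendix 1 then classes it as unresolved.

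**Working it through.** **Inputs.** Collapse rules and censoring rule: Appendix 1. Duration = last date − first date + 1: Section 8. The subject dates below are invented for illustration.

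**The plan's own example.** Records run 1-5, 6-11 and 10-12 January. The second starts one day after the first ends (contiguous). The third starts within the second (overlapping). Result: one cluster, 1-12 January, 12 − 1 + 1 = 12 days. This reproduces the SAP.

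**What the text implies about ranking.** The maximum runs over all clusters, and the censoring rule gives every unresolved cluster an end date. Every cluster therefore has a length, and the longest is selected. The rule is implicit but readable.

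**Displacement on that reading.**
- Cluster 1: 1 March to 30 April, resolved. 31 + 30 = 61 days.
- Cluster 2: from 1 June, ongoing or fatal, last known alive 20 June. 20 − 1 + 1 = 20 days, censored.
- Listed: cluster 1, 61 days, resolved.

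The lengths tie when the last known alive date is 31 July (30 + 31 = 61 days). From 1 August the censored cluster is listed. Displacement therefore needs follow-up after the second onset to be shorter than the whole first episode.

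**Three readings compared.** The resolved cluster is 1 January to 28 February (31 + 28 = 59 days) in each case.

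| Later cluster | Its length | Rank by length | Resolved clusters only | Unresolved first |
|---|---|---|---|---|
| Fatal, 20-29 March | 10 days | 59 resolved | 59 resolved | 10 censored |
| Ongoing from 20 March, alive 8 April | 12 + 8 = 20 days | 59 resolved | 59 resolved | 20 censored |
| Ongoing from 20 March, alive 1 July | 12 + 30 + 31 + 30 + 1 = 104 days | 104 censored | 59 resolved | 104 censored |

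Only ranking by length matches the text as written. The other two set aside either its reference to all clusters or its word longest.

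**Grade 3-5 listing.** Appendix Table 1 drops clusters without a grade 3-5 record. A fatal cluster can be displaced there only if the resolved cluster also reached grade 3 or higher. If the resolved cluster was grade 2 at most, the fatal one is listed.

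**Where the displaced event still appears.** 7.6.7 calls for a by-subject listing of all IMAEs, not limited to the longest cluster. The event also counts in the 7.6.7 worst-grade summaries, in the grade 5 column if fatal. 7.6.1 lists and tabulates deaths.

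**Frequency.** The SAP gives no rate of repeat clusters and no distribution of their durations. Any percentage would rest wholly on assumed inputs, so none is given.

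**Section 8 against Appendix 1.** Take a 31-day month in which the subject dies and an event is recorded as resolved, day missing. The imputed resolution is day 31. For death on days 1 to 30 it falls after death and is pulled back. If the death date is used, it equals the death date and the event becomes unresolved. For death on day 31 the two dates coincide with no adjustment. If an earlier last known alive date is used instead, the event stays resolved. So the clash needs a missing day, resolution in the month of death, and a final date equal to the death date. It changes a status flag towards the less favourable reading.

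**The case for a change.** The strongest argument for a change is that this listing is the only specified output for time to resolution of immune-related events, that two programmers could rank clusters differently, and that a sentence or two would settle it. A status column attached to the selected cluster would not reveal that another cluster in the same category is still open.

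Some of this stands. Appendix 1 leaves the ranking implicit and has no tie rule, and a reader who looks only at the longest-cluster listing will not see a shorter open episode.

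The rest carries less weight. The listing announces itself as showing the longest cluster, and a 61-day cluster that resolved is correctly shown as resolved. The lower-bound argument matters for estimating the distribution of each subject's maximum, which this SAP never does. The obvious remedy, reporting 61 days as censored because another cluster is open, would attach one cluster's status to another's duration and make the row wrong for the cluster it describes. Tie-breaking is ordinary programming detail. Section 9 leaves listing layouts to the Data Presentation Plan, which is not at hand, so whether status or further clusters are displayed cannot be judged here.

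**Conclusion.** The observation is correct, but it does not call for a change to the SAP. Read plainly, Appendix 1 ranks clusters by observed length, with unresolved ones ended at the last known alive date. A longer resolved cluster can therefore be listed ahead of a shorter ongoing or fatal one. The reach is two by-subject listings in an abbreviated report, for subjects with at least two separate clusters in a category, and it is narrower still in the grade 3-5 listing. No estimate, test or summary table depends on the selection, and the displaced event remains in the other IMAE and death outputs.

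This conclusion assumes that time to resolution stays a listing and that the full IMAE listing is produced as planned. If a median or Kaplan-Meier analysis were added later, the ranking of censored clusters would need to be fixed first. As the plan stands, showing each cluster with its own duration and status is a sensible programming choice that needs no amendment. The Section 8 overlap is a separate, rare clerical matter that analysts can settle when they derive the dates.
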